|  | 
Patients will be stratified according to tumor histology (squamous vs non-squamous) and smoking history (current smoker, former smoker, and never smoker). Current smokers will include subjects with any tobacco use, former smokers will include subjects with a history of tobacco use who do not currently use any tobacco, and never smokers will include subjects who have never used any tobacco products.
 
Patients will be randomized in a 1:1 ratio into 1 of 2 treatment arms.
 
 
• Arm 1: Patients will receive AM0010 as a subcutaneous (SQ) daily (QD) injection and nivolumab as intravenous (IV) infusion on Day 1 of a 14-day cycle or on Day 1 of a 28-day cycle, at the decision of the Investigator.             
 
○ AM0010 Dose 
 
▪ ≤80 kg body weight = 0.8 mg
 
▪ >80 kg body weight = 1.6 mg
 
 
 
○ Nivolumab Dose 
 
▪ 240 mg over approximately 30 minutes IV infusion every 2 weeks (Q2W)
 
 
 
or
 
▪ 480 mg over approximately 30 minutes IV infusion every 4 weeks (Q4W)
 
 
 
• Arm 2: Patients will receive nivolumab as IV infusion on Day 1 of a 14-day cycle or on Day 1 of a 28-day cycle, at the decision of the Investigator.             
 
○ Nivolumab Dose 
 
▪ 240 mg over approximately 30 minutes IV infusion Q2W
 
 
 
or
 
▪ 480 mg over approximately 30 minutes IV infusion Q4W
 
 
 
 
Crossover of patients from nivolumab Q2W schedule to Q4W schedule during the study is acceptable. A complete nivolumab cycle (4 weeks; ie 2 doses of nivolumab 240 mg in a cycle) should be completed before such crossover. Trial sites will provide best supportive care per institution’s standard of care including concomitant medications.
 
Arms 1 and 2 dosing (QD for AM0010 and Q2W or Q4W for nivolumab) will continue in the absence of disease progression, unacceptable toxicity, start of new anticancer treatment, or the patient withdraws consent, whichever is first.
 
At the time of documented disease progression (per Investigator assessment), patients in Arm 1 will be discontinued from the treatment period of the trial and patients in Arm 2 may crossover to receive treatment with AM0010 with nivolumab.
 
All randomized patients will be followed for OS every 8 weeks (±7 days) during the first year from the 90-day follow-up visit, every 12 weeks (±7 days) during the second year, and every 16 weeks (±7 days) thereafter. The survival follow-up will be done until death or the study completion (see Section 3.6), whichever is first, whether or not trial drug was administered. For patients who were randomized, but withdraw consent, survival (date of death) will be obtained by use of publicly available information.
 
Tumor assessment will be performed for all randomized patients every 8 weeks (±7 days) during the study treatment and during the first year from discontinuation of the study treatment, every 12 weeks (±7 days) during the second year, and every 16 weeks (±7 days) thereafter. Tumor assessment will be repeated until disease progression, death, or receipt of new anti-cancer therapy, or until study completion, whichever is first, whether or not study treatment was administered.
 
All computed tomography (CT)/magnetic resonance imaging (MRI) scans for all randomized patients enrolled on the trial will be collected prospectively and submitted to a central imaging vendor for archiving. These scans may be independently reviewed at a later time at the request of Eli Lilly and Company
 |

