In the study in non-squamous NSCLC, the median OS was 12.2 months among patients in the nivolumab group as compared to 9.4 months among the 290 patients in the docetaxel group; HR 0.72, p=0.002. The 18-month OS rate was 39% with nivolumab vs 12% with docetaxel. Although the progression-free survival (PFS) did not favor nivolumab over docetaxel (median 2.3 months and 4.2 months, respectively), the rate of PFS at 1 year was higher with nivolumab than with docetaxel (19% and 8% respectively). Nivolumab was associated with greater efficacy than docetaxel across all end points in subgroups defined according to pre-specified levels of tumor-membrane expression ( $\geq 1\%$ ,  $\geq 5\%$ , and  $\geq 10\%$ ) of PD-L1. Treatment-related adverse events (TRAEs) of Grade 3 or 4 were reported in 10% of the patients in the nivolumab group (Borghaei, Paz-Ares et al. 2015).

Patients with advanced squamous-cell NSCLC who have disease progression during or after first-line chemotherapy were treated in a Phase 3 randomized study evaluating the efficacy and safety of nivolumab as compared with docetaxel in this patient population ((Brahmer, Reckamp et al. 2015). The OS was 9.2 months with nivolumab vs 6.0 months with docetaxel; HR 0.59,  $p < 0.0001$ . At 1 year, the OS rate was 42% with nivolumab vs 24% with docetaxel. The response rate was 20% with nivolumab vs 9% with docetaxel ( $p = 0.008$ ). The median PFS was 3.5 months with nivolumab vs 2.8 months with docetaxel (HR 0.62,  $p < 0.0001$ ). The expression of the PD-1 ligand was neither prognostic nor predictive of benefit. Treatment-related adverse events of Grade 3 or 4 were reported in 7% of the patients in the nivolumab group as compared with 55% of those in the docetaxel group.

Nivolumab is Food and Drug Administration (FDA)-approved as a single agent for the treatment of patients with metastatic NSCLC with progression on or after platinum-based chemotherapy. Combining AM0010 with nivolumab may present a promising therapeutic combination to address this unmet medical need in patients with advanced NSCLC.

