In this cohort, 4 of the 5 patients were evaluated for PD L1 expression in the tumor, and all were negative for PD-L1 (<1% PD-L1-positive tumor cells), including both patients who had a PR.

Most patients enrolled in the escalation cohorts and expansion cohorts had previously progressed during or following multiple lines of therapy. Despite this fact, very encouraging objective tumor responses have been observed in most combination therapies with AM0010.

The median PFS was 10.9 months (range 4.7-19.3+), the median OS has not been reached; 80% of patients who received AM0010 at 1 mg (10 µg/kg) plus pembrolizumab were alive with a median follow-up of 25.2 months (range 24.5-26.9+).

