## **7.8 Continued Treatment**

### **7.8.1 Crossover**

At the time of disease progression (as assessed by the Investigator) patients randomized to trial Arm 2 may crossover to study Arm 1 to receive AM0010 and nivolumab. When progressive disease is noted on the scan for an ARM 2 patient, no more than 21 days should pass before the patient crosses over to ARM 1. The scans and/or clinical assessment at crossover will be used as a new baseline to determine response or PD on ARM 1.

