### 6.6.2. Adverse Events

Adverse event (AE) terms will be mapped using the Medical Dictionary for Regulatory Activities (MedDRA). Adverse events will be graded according to the National Cancer Institute (NCI) – A Common Terminology Criteria for Adverse Events (CTCAE) v 4.03.

Pre-existing conditions are defined as AEs that begin prior to the first dose of study drug.

A treatment emergent adverse event (TEAE) is defined as any AE that begins between the day of first dose and 30 days after treatment discontinuation (or up to any time if serious and related to study treatment), or any pre-existing condition that increases in CTCAE grade between the day of first dose and 30 days after treatment discontinuation (or up to any time if serious and related to study treatment).

Related AEs in patients treated with AM0010 in combination with nivolumab are defined as either related to AM0010 or related to nivolumab or both AM0010 and nivolumab.

The following TEAE/serious adverse events (SAE) outputs will be produced:

- a. overview of TEAEs
- b. summary of TEAEs by Preferred Terms (PTs) (all grade and grade  $\geq 3$ )
- c. summary of TEAEs by System Organ Class (SOC) and PT (all grade and grade  $\geq 3$ )
- d. summary of TEAEs by PT and Maximum Grade
- e. listing of SAEs
- f. summary of SAEs by SOC and PT (all grade and grade  $\geq 3$ )
- g. listing of TEAEs leading to study treatment discontinuation

Summaries b, c, d, and f will be produced for the related TEAEs/SAEs.

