#### **6.7.4. Crossover Patients**

Patients in Arm 2 (nivolumab) who crossover to Arm 1 (AM0010 in combination with nivolumab) following documented disease progression will be analyzed accordingly if data warrants.

For patients who crossover to Arm 1 after documented disease progression on nivolumab, time to progression while on nivolumab and time to progression following progression will be estimated, where the time to progression following crossover is defined as the time from time of crossover to the earliest documented disease progression. The last available tumor assessment before crossover will serve as the baseline for disease assessment post crossover. If the number of events permits, time to progression before and after crossover will be summarized descriptively using the Kaplan-Meier method

Patients who crossover to the AM0010 in combination with nivolumab are censored at time of crossover (i.e., AEs occurring during treatment with AM0010+nivolumab are excluded for control arm (nivolumab) patients). An exploratory safety analysis may be conducted for the crossover patients including all adverse events starting from the date of first dose of AM0010+nivolumab.

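### Control-arm adverse events are censored at crossover, but the AE tables are crude percentages that take no account of censoring or time at risk

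*SAP*

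**What the plan says.** SAP 6.7.4 treats Arm 2 patients who move to the combination as censored at that moment, with the consequence that "AEs occurring during treatment with AM0010+nivolumab are excluded for control arm (nivolumab) patients". It concerns "Patients in Arm 2 (nivolumab) who crossover to Arm 1 (AM0010 in combination with nivolumab) following documented disease progression". Protocol 7.8.1 sets the timing: after a scan shows progression, "no more than 21 days should pass before the patient crosses over to ARM 1".

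SAP 6.6.2 defines a treatment-emergent event (TEAE) as "any AE that begins between the day of first dose and 30 days after treatment discontinuation", with no end date for events that are both serious and related. Its outputs start with an "overview of TEAEs" and continue with summaries by term, organ class and grade, plus listings. SAP 6.1.2 makes categorical summaries counts and percentages of the population analysed. No AE output uses person-time or time to first event.

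For Arm 1, the protocol synopsis says that at documented progression "patients in Arm 1 will be discontinued from the treatment period of the trial". Those patients then keep the full 30-day window.

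Treatment duration is tabulated by arm in SAP 6.6.1.1, but not as a denominator for AEs. SAP 4.2 makes safety and tolerability of the combination versus nivolumab a secondary objective, and SAP 6.1.1 makes all analyses descriptive.

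**The concern.** Censoring has a meaning only for an estimator that uses time at risk. In a crude percentage, the censored patient still counts as one whole patient below the line and can contribute nothing more above it. The two AE columns therefore rest on different observation windows, and nothing planned beside them separates a difference in event rate from a difference in time observed.

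The comparison matters because it serves a secondary objective. Protocol 6.4.5 provides for no data monitoring committee, and SAP 6.8 allows interim looks for safety, so these tables would be the main between-arm evidence on AEs.

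**Working it through.** **The plan's own figures.** The documents give no AE incidence, crossover share or expected exposure to reproduce. The only design figures are the 90% intervals for response in SAP 5.2. Exact Clopper-Pearson limits with n = 25 reproduce them: 3.3-28.2%, 11.0-42.0% and 17.0-50.4% for 3, 6 and 8 responders. They are used below only as a yardstick of precision.

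**What the cut removes.** An Arm 1 patient who stops at progression is counted for 30 more days. An Arm 2 patient who crosses over 0 to 21 days after treatment would otherwise have stopped loses 30 - 0 = 30 down to 30 - 21 = 9 days, plus later related serious events.

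**Inputs from the documents.** Median PFS on nivolumab, used as a proxy for time on treatment: 2.3 months in non-squamous disease and, in squamous disease, "The median PFS was 3.5 months with nivolumab vs 2.8 months with docetaxel" (protocol 1.1). Tail: 30 days / 30.4375 = 0.986 month; 21 days = 0.690 month.

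**Assumptions not in the documents.** Exponential time to progression; a constant AE hazard λ, identical in both arms, of 0.05 to 0.4 per month; crossover share 25% to 100%.

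**Formula.** With h = ln 2 / median,

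P(at least one AE) = 1 - [h/(h + λ)] × exp(-λ × tail).

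The tail is 0.986 month for Arm 1 and for Arm 2 patients who do not cross over. It is 0 or 0.690 month for those who do.

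**Cut alone: equal medians, λ = 0.10, 50% crossover.** For median 2.3 months, h = 0.301 and h/(h + λ) = 0.751.
- Arm 1: 1 - 0.751 × 0.906 = 32.0%.
- Crossover patients with no gap: 1 - 0.751 = 24.9%. Arm 2 = (32.0 + 24.9)/2 = 28.4%.
- Crossover patients with a 21-day gap: 1 - 0.751 × 0.933 = 29.9%. Arm 2 = 30.9%.

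| Median, both arms | Gap to crossover | Arm 1 | Arm 2 | Difference (points, unrounded inputs) |
|---|---|---|---|---|
| 2.3 months | 0 days | 32.0% | 28.4% | 3.5 |
| 2.3 months | 21 days | 32.0% | 30.9% | 1.0 |
| 3.5 months | 0 days | 39.8% | 36.7% | 3.1 |
| 3.5 months | 21 days | 39.8% | 38.9% | 0.9 |

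The largest, 3.5 points, is 0.035 × 25 = 0.9 patient. Over the whole grid the range is 0.3 points (λ = 0.05, 25% crossover, 21-day gap, median 3.5) to 14.0 points (λ = 0.4, 100% crossover, no gap, median 2.3), the latter being 3.5 patients in 25.

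**Unequal treatment time, same λ = 0.10.**
- Arm 1 median 7 months, Arm 2 median 3.5: 54.9% vs 39.8% with no crossover cut, or 15.1 points. With 50% crossover and no gap, 54.9% vs 36.7%, or 18.2 points. The cut adds 3.1.
- Arm 1 median 2.3, Arm 2 median 3.5, same cut: 32.0% vs 36.7%, so Arm 1 looks 4.7 points less toxic.

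**Does a time-at-risk measure repair this?** Under a constant hazard, yes: simulated first-event rates were 0.100 vs 0.100 per patient-month with equal medians of 2.3 or 3.5 and with 7 vs 3.5. Under early clustering, the rate alone does not. Take a hazard of 0.4 per month in month 1 and zero afterwards in both arms, with follow-up to progression and no tail. Let s = 0.4 + h.
- Crude incidence = (0.4/s)(1 - e^(-s)): 30% at median 2.9 (midpoint of 2.3 and 3.5), 31% at 5 and 32% at 10.9.
- Time at risk = (1 - e^(-s))/s + e^(-s)/h: 2.95, 4.98 and 10.69 months.
- Rates: 0.2956/2.947 = 10.0, 0.3093/4.983 = 6.2 and 0.3201/10.69 = 3.0 per 100 patient-months, although the hazards are identical.

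A time-to-first-event estimate has the same target in both arms here: 1 - e^(-0.4) = 33% at one month.

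**The case against.** The best defence is that the crossover cut is right in itself: it keeps combination-period events out of the nivolumab column. Exposure is tabulated separately, laboratory grades are summarised by cycle, no safety test is planned, and SAP 6.7.4 allows a separate look at events after crossover. All of that stands. It limits the point to interpretation, but separate exposure tables do not adjust the AE percentages.

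A reader might go further and infer that Arm 1 is followed without limit while Arm 2 is cut, so that AM0010 must look more toxic, by tens of points. The documents do not support this. Arm 1 treatment also ends at progression, with TEAEs counted for 30 more days, so both arms are observed to about the same milestone. A calculation such as λ/(λ + ln 2/median) with λ = 0.10 gives 29.5% at 2.9 months against 41.9% at 5 and 61.1% at 10.9, or 12 to 32 points. It contains no crossover term, however, and returns zero when the medians are equal. The 5 months is an assumption, and the 10.9 comes from five patients on AM0010 with pembrolizumab (protocol 1.2.3.1). Capping follow-up at 6 months, the limiting case for the last patients at the SAP 6.8 cut-off, gives 26% vs 32-38%, or 6 to 13 points.

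Nor is the direction fixed. Protocol 6.4 stops both Arm 1 drugs when one is discontinued, which can shorten Arm 1 exposure.

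One consideration runs the other way. Protocol 7.6 lets patients continue past initial progression. An Arm 1 patient who stays on until a rescan at 4 weeks is counted for at least 28 + 30 = 58 days after first progression, against at most about 21 for an Arm 2 patient who crosses over promptly. The documents give no frequency for this, so it cannot be sized.

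**Conclusion.** The point holds in a limited form. The plan censors Arm 2 AEs at crossover and then reports them with a measure that cannot take account of censoring. With equal AE rates and equal time to progression, this alone raises Arm 1 by roughly 1 to 3.5 points at an assumed 0.10 per month and 50% crossover, under one patient in 25, and by 0.3 to 14 points over the wider assumed grid. For scale, the SAP's own 90% interval for 8 of 25 runs from 17% to 50%.

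Unequal treatment time can matter more. It would make Arm 1 look worse if treated longer and better if stopped early, and it is not caused by the crossover rule. These sizes rest on exponential times, a constant common hazard, PFS as a proxy for treatment time, and crossover shares that the documents do not give. No test or efficacy result is affected.

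**What to change.** In SAP 6.6.2, keep the crude tables, and keep the crossover cut of SAP 6.7.4. For any TEAE, Grade 3 or higher, related and serious TEAEs, add by arm:

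- a time-to-first-event cumulative incidence estimate, with time at risk ending at crossover or at the end of the TEAE window;
- beside it, the exposure-adjusted rate: patients with a first event per 100 patient-months at risk.

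State one end-of-window rule for both arms, including for serious related events, whose window is now open-ended. Footnote that the rate assumes a constant hazard and can mislead if events cluster early, which is why it should not stand alone.

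The cost is a little more programming on dosing, crossover and event-onset dates that the planned analyses already need. The estimates will be imprecise with about 25 patients per arm. Because crossover follows progression, the time-to-event estimate also assumes that patients censored there had the same AE hazard as those still observed.

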#### **6.8. Timing of Planned Analyses**

Interim analysis may be conducted to evaluate patient's safety. Efficacy data will be described without performing any formal statistical test. The primary analysis (data cut off) will occur 6 months after the last patient randomized.

